#### 8.8 Sponsor Protocol Deviation Reporting

A Protocol Deviation is defined as any non-compliance with the clinical trial Protocol, Manual of Operational Procedures (MOP) and other Sponsor approved study related documents, GCP, or protocol-specific procedural requirements on the part of the participant, the Investigator, or the study site staff inclusive of site personnel performing procedures or providing services in support of the clinical trial.

It is the responsibility of the study Staff to document any protocol deviation identified by the Staff or the site Monitor in the CCR Protocol Deviation Tracking System (PDTS) online application. The entries into the PDTS online application should be timely, complete, and maintained per CCR PDTS user requirements.

In addition, any deviation to the protocol should be documented in the participant's source records and reported to the reviewing IRB per their guidelines. OSRO required protocol deviation reporting is consistent with E6(R2) GCP: Integrated Addendum to ICH E6(R1): 4.5 Compliance with Protocol; 5.18.3 (a), and 5.20 Noncompliance; and ICH E3 16.2.2 Protocol deviations.

### 9 CLINICAL MONITORING

Clinical site monitoring is conducted to ensure:

- that the rights of the participants are protected;
- that the study is implemented per the approved protocol, Good Clinical Practice and standard operating procedures; and,
- the quality and integrity of study data and data collection methods are maintained.

Monitoring for this study will be performed by NCI CCR Office of Sponsor and Regulatory Oversight (OSRO) Sponsor and Regulatory Oversight Support (SROS) Services contractor. Clinical site monitoring activities will be based on OSRO standards, FDA Guidance E6(R2) Good Clinical Practice: Integrated Addendum to ICH E6(R1) March 2018, and applicable regulatory requirements.

Details of clinical site monitoring will be documented in a Clinical Monitoring Plan (CMP) developed by OSRO. CMPs will be protocol-specific, risk-based and tailored to address human subject protections and integrity of the study data. OSRO will determine the intensity and frequency of monitoring based on several factors, including study type, phase, risk, complexity, expected enrollment rate, and any unique attributes of the study and the site. The Sponsor will conduct a periodic review of the CMP to confirm the plan's continued appropriateness. A change to the protocol, significant or pervasive non-compliance with GCP, or the protocol may trigger CMP updates.

OSRO SROS Monitoring visits and related activities will be conducted throughout the life cycle of each protocol. The first activity is before the study starts to conduct a Site Assessment Visit (SAV) (as warranted), followed by a Site Initiation Visit (SIV), Interim Monitoring Visit(s) (IMVs), and a study Close-Out Visit (COV).

Some monitoring activities may be performed remotely, while others will occur at the study site(s). Monitoring visit reports will describe visit activities, observations, and associated action items or follow-up required for resolution of any issues, discrepancies, or deviations. Monitoring reports

Version Date: 7/10/2025

will be distributed to the study PI, NCI CCR QA, CCR Protocol Support Office, coordinating center (if applicable), and the Sponsor regulatory file.

The site Monitor will inform the study team of any deviations observed during monitoring visits. If unresolved, the Monitor will request that the site Staff enter the deviations in the CCR Protocol Deviation Tracking System (PDTS) for deviation reporting to the Sponsor and as applicable per institutional and IRB guidance.

## 10 STATISTICAL CONSIDERATIONS

### 10.1 OBJECTIVES AND ENDPOINTS

OBJECTIVES	ENDPOINTS	JUSTIFICATION FOR ENDPOINTS
Primary		
To determine the single agent antitumor activity (disease control rate) of the anti-superenhancer agent Minnelide in participants with advanced, previously treated ASCP	Assess disease control rate in the study population, where disease control = best response of CR, PR or at least 16 weeks of stable disease	Establishing disease control in 8 or more of 25 participants with advanced previously treated ASCP would be considered clinically significant.
Secondary		
Determine Minnelide safety in participants with advanced, previously treated ASCP	Identify Adverse Events of grade 2 and above (per CTCAE criteria, version 5.0) related to Minnelide that occur from start of treatment to 30 days after last treatment.	Descriptive endpoint to assess toxicity profile of the study drug in this population.
	Assess rate of Serious Adverse Events related to Minnelide that occur from start of treatment to 30 days after last treatment.	
Assess alternative measures of anti- tumor activity	Determine median time until disease progression, switch to a new systemic treatment or death in the treated population. Data cut-off will occur 1 year after last Minnelide treatment.	Descriptive endpoints that may help to determine sample size needed for future Phase 3 study
	Determine median time until death in the treated population. Data cut-off will occur 1 year after last Minnelide treatment.	
	Determine objective response rate of Minnelide.	

OBJECTIVES	ENDPOINTS	JUSTIFICATION FOR ENDPOINTS
Exploratory		
Identify factors that influence participant response to treatment through detailed molecular analysis of participant tumor, serum and blood cell samples acquired at baseline, on-treatment and at time of progression	For each patient with available samples, we will describe the following properties and consider associations with patient response to therapy:	These endpoints have been selected to help understand why the drug may or may not work, to allow better design of future studies in this patient population.
	Tumor genetic mutations at baseline and at time of progression	Do specific genetic profiles give a patient higher or lower likelihood or response? Does treatment change mutational profile?
	Treatment-related change (between pre-treatment baseline and ~C1D15) in:	
	1) protein expression of Myc in tumor cells, 2) protein expression HSP70 in tumor cells and 3) change in accessibility of tumor cell chromatin	Has the drug reached the tumor? Is predicted bioactivity seen?
	4) Populations and locations of tumor infiltrating immune cells, 5) circulating cytokines (as above and at time of progression), and 6) circulating immune cell subsets (as above, start of C2 and at time of progression)	Does Minnelide change the host and/or tumor immune environment?
	7) Change in tumor-associated cell milleu with Minnelide treatment	Does Minnelide alter the tumor microenvironment?
	Changes in CTCs at baseline, ~C1D15, start of C2 and at time of progression	Does Minnelide clear CTCs?

Version Date: 7/10/2025

OBJECTIVES	ENDPOINTS	JUSTIFICATION FOR ENDPOINTS
Evaluate ctDNA as a marker of response in ASCP	Percent of patients with detectable KRAS mutant ctDNA; and, concordance in change of detectable KRAS mutant ctDNA and disease control status as assessed at baseline, ~C1D15, start of C2, and at time of progression.	KRAS mutation is nearly ubiquitous in this population and mutant ctDNA may serve as a reliable early bloodbased biomarker of response. This aim is hypothesisgenerating

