## **Design:**

- This is a phase II single cohort clinical trial with one arm.
- The number of evaluable participants needed for the primary endpoint is 25; maximum accrual set at 55 participants (accounting for screen failures and inevaluable participants).
- Initial participants will receive Minnelide at 2 mg/day PO on Days 1-21 of a 28 day cycle. Later participants will receive a higher dose of 2.5 mg/day PO on the same schedule.
- Treatment will be continued for up to 12 cycles (1 year) in the absence of disease progression or unacceptable toxicity.
- Treatment response will be assessed by imaging every 2 cycles (8 weeks).
- Optional tumor biopsies will be requested mid-cycle 1 and at time of progression.
- A disease control rate of  $\geq 40\%$  in this highly refractory population would constitute a positive study. Up to 12 participants will treated be initially. If 3 of the 12 participants have a response, then up to 13 additional participants will be entered to determine the true response rate.

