There have been 6 patients that have discontinued the study drug due to a treatment emergent adverse event (TEAE). Four instances were considered Grade 5 (as described above), one was Grade 3, one was Grade 2. One of the TEAE's were considered to be probably related to use of the study drug, three possibly related (Two Grade 5 sepsis, one Grade 3 hypokalemia, one Grade 2 neutrophil count decrease), and the other two not related (Grade 5 disease progression). A total of 56 Serious Adverse Events have occurred in 33 patients and 11 were found to be related to the investigational product. The 11 related SAE's, two grade five sepsis, a grade four sepsis, a grade three nausea, a grade three polymicrobial bacteremia, a grade three intractable nausea, a grade three hypokalemia event, a grade three worsening leukocytosis, a grade three blood infection, and a grade two enteritis were on the monotherapy regimen. A grade five sepsis and a grade two esophagitis were on the combination therapy regimen. Overall, the most commonly reported TEAE (> 20%) regardless of grade or causality have included: Anemia, Abdominal Pain, Anorexia, Vomiting, Diarrhea, Nausea, Fatigue, Hypokalemia, and Hypoalbuminaemia. 22 patients had at least 1 AE that was considered definitely, probably, or possibly related to the study drug. Grade 3 – Grade 5 TEAE's reported in  $\geq$  3% of patients regardless of causality to data are as follows:

- Grade 3 Adverse Events: Abdominal Pain 10%, Anemia 15%, Alkaline Phosphatase Increased 4%, Dehydration 3%, Diarrhea 6%, Hypoalbuminemia 6%, Hypokalemia 10%, Hyponatremia 6%, Nausea 3%, Neutrophil Counts Decreased 13%, Platelet Count Decreased 3%, Thrombocytopenia 3%, Urinary Tract Infection 3%, Vomiting 3%, Weight decreased 3%, White Blood Cell Count Decreased 3%.
- Grade 4 Adverse Events: Leukopenia 3%, Neutropenia 7, Sepsis 3%.
- Grade 5 Adverse Event: Disease Progression 9%

Of note, no cerebellar toxicity has been observed with the oral formulation.

Pharmacokinetic data was obtained in 33 patients receiving oral Minnelide at seven different dose levels from 0.50 mg/day to 2.00 mg/day. Peak triptolide drug levels were observed within 60

[figure not shown]
Version Date: 7/10/2025

minutes after administration of the oral dose in 26 of 31 patients. No serum triptolide was detected by 240 minutes post-administration in all 23 patients with data at this timepoint.

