## 8.1.5 Relationship to Study Product

All AEs will have their relationship to study product assessed using the terms: related or not related.

- Related There is a reasonable possibility that the study product caused the adverse event.
   Reasonable possibility means that there is evidence to suggest a causal relationship between the study product and the adverse event.
- Not Related There is not a reasonable possibility that the administration of the study product caused the event.

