## 8.2 ASSESSMENT OF SAFETY EVENTS

AE information collected will include event description, date of onset, assessment of severity and relationship to study product and alternate etiology (if not related to study product), date of resolution of the event, seriousness and outcome. The assessment of severity and relationship to the study product will be done only by those with the training and authority to make a diagnosis and listed on the Form FDA 1572 as the site principal investigator or sub-investigator. AEs occurring during the collection and reporting period will be documented appropriately regardless of relationship. AEs will be followed through resolution.

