### **10.5.4 Safety Analyses**

The fraction of participants who experience a toxicity, by grade and type of toxicity, will be tabulated.

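### The only SAE rate the plan specifies counts events called related to Minnelide; add all-cause safety tables beside it and reconcile 10.1 with 10.5.4

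*Combined protocol and SAP*

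**What the plan says.** The secondary objective in 1.1.2 is the overall safety of Minnelide in this population. Section 10.1 turns it into two endpoints. The first is "Identify Adverse Events of grade 2 and above (per CTCAE criteria, version 5.0) related to Minnelide"; the second is "Assess rate of Serious Adverse Events related to Minnelide that occur from start of treatment to 30 days after last treatment". Both are filtered by attribution.

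On how attribution is made, section 8.1.5 says: "All AEs will have their relationship to study product assessed using the terms: related or not related". Section 8.2 gives the task to the principal investigator or sub-investigators listed on the Form FDA 1572. There is no comparator; the précis says: "This is a phase II single cohort clinical trial with one arm".

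The planned safety analysis in 10.5.4 is one sentence: "The fraction of participants who experience a toxicity, by grade and type of toxicity, will be tabulated". It does not define toxicity, state an attribution rule or mention seriousness. Nothing else in section 10 specifies an all-cause SAE rate.

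Collection is wider than the endpoints. Section 8.2 says: "AEs occurring during the collection and reporting period will be documented appropriately regardless of relationship". It also has SAEs captured in the clinical database. The exception is in 6.1: grade 1 or 2 laboratory abnormalities judged unrelated are entered only under listed conditions.

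**The concern.** With a control arm, all-cause rates can be compared and attribution matters little. With one arm, a related-only rate depends on each event being assigned correctly, by assessors who know that every participant takes the drug. Section 12.3.1.1 names myelosuppression, febrile neutropenia and neutropenic sepsis as the main toxicities. Whenever such an event is wrongly put down to the cancer, it leaves both 10.1 endpoints and the rate is biased low.

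Two things are at stake. First, the stated objective is overall safety, but the only SAE rate specified is the attributed one. By November 2022 only six patients had been treated at 2.5 mg in the oral Phase 1 trial (1.2.2.2.2), so this trial will add materially to what is known at that dose. Second, the common-event frequencies in 1.2.2.2.1 and 1.2.2.2.2, and the grade 3-5 frequencies in the latter, are given whatever the cause. Related-only adverse-event results here cannot be set against them.

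**Working it through.** The plan states no percentage, sample size or power for safety, so there is no plan figure to reproduce. The check asks how much of the SAE total a related-only count leaves out, using the protocol's own Phase 1 summaries.

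**Inputs**
- IV Phase 1 (1.2.2.2.1): 28 SAEs in 17 patients, 6 related.
- Oral Phase 1 (1.2.2.2.2): "A total of 56 Serious Adverse Events have occurred in 33 patients and 11 were found to be related to the investigational product".
- Sensitivity input: the oral summary states 11 related SAEs but itemises 10 on monotherapy and 2 on the combination, 12 in all.

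**Formula:** share left out = (all SAEs − related SAEs) / all SAEs.

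| Source | Calculation | Left out |
|---|---|---|
| IV | (28 − 6)/28 = 22/28 | 78.6% |
| Oral, stated count | (56 − 11)/56 = 45/56 | 80.4% |
| Oral, itemised count | (56 − 12)/56 = 44/56 | 78.6% |
| Pooled, stated count | (84 − 17)/84 = 67/84 | 79.8% |

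Every variant lies between 78.6% and 80.4%. As a ratio, the all-cause count was 28/6 = 4.7 times the related count in the IV trial and 56/11 = 5.1 times in the oral trial.

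**How steady is attribution in the protocol's own text?** Three comparisons of the oral Phase 1 summaries bear on this.
- The combination-regimen grade 5 sepsis is called unrelated to Minnelide in one paragraph of 1.2.2.2.2 and appears in the list of related SAEs in the next.
- The same section reports one related sepsis death on monotherapy, but its list of related SAEs has two grade 5 sepsis events on monotherapy.
- Participants with at least one related adverse event number 22 in 1.2.2.2.2 and 43 in 14.1.2, for what appears to be the same 67 patients (33% and 64%). One may be a drafting slip, since 43 is also the monotherapy headcount.

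The all-cause total, 56 SAEs in 33 patients, is the same in both sections.

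**Does 10.5.4 already cover unrelated events?** Section 3.3.4 uses toxicity for events that are then divided into attributable and unrelated, and section 3.3 adds a drug-related qualifier when it means only those. So 10.5.4 can be read as all-cause by grade and type. Section 10.1 cannot. On either reading, 10.5.4 gives no rate by seriousness.

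**The case against.** The strongest reply is that 10.5.4 has no attribution filter and no grade floor, that the protocol elsewhere uses toxicity to include unrelated events, and that 10.4.1 makes every treated participant evaluable. An all-cause grade-by-type table may therefore already be intended. This stands in part. It would supply much of what is asked for grades 3-5. It supplies no SAE rate and leaves 10.1 and 10.5.4 unreconciled.

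Second, a reader might infer from the 80% that the trial would understate drug toxicity by that much, or about fivefold. The documents do not support this. The 80% is every SAE called unrelated, and some of those were disease progression: section 1.2.2.2.1 reports progression deaths, and 1.2.2.2.2 gives grade 5 disease progression at 9%. No misattribution rate is stated or can be derived.

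Third, a reader might infer that unrelated serious events will be lost. They will not: 8.2 records them, and 8.4 waives only expedited reporting of progression events.

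Fourth, attribution is not unreviewed. The principal investigator reviews each participant's events (7.4.1), SAEs go to the sponsor's safety office for assessment (8.3), and the sponsor applies its own causality standard for regulatory reports (8.7). This stands, but nothing says that these later reviews change the call used for the endpoint.

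Fifth, the Phase 1 text also gives related SAE counts, so a related SAE result here has something to be compared with. The gap concerns the all-cause event frequencies only.

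Finally, section 12.3.3 puts median survival at no more than 3 months, so an all-cause SAE rate will be mixed with progression, and all deaths already count in overall survival. This is fair, and it is why progression events need their own line.

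**Conclusion.** The point holds as a gap in the specified safety analysis. Both 10.1 endpoints are related-only, no all-cause SAE rate is planned, and 10.1 and 10.5.4 do not say the same thing. The attributed SAE rate errs low whenever a drug event is assigned to the disease.

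The size that can be stated is the endpoint's dependence on attribution: about 79-80% of SAEs in the two Phase 1 trials would fall outside it. The size of any bias is unknown. Carrying the 79-80% to this trial is an assumption. The counts are per event and not per participant. The oral trial included 24 combination patients among its 67. It also described related adverse events as definite, probable or possible, where this trial uses two levels.

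The safety endpoints are descriptive. No hypothesis, decision rule or sample size rests on them, and the primary endpoint is untouched. This is a cheap improvement to the analysis plan.

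**What to change.** In 10.1 and 10.5.4, state that treatment-emergent grade 3-5 adverse events, SAEs and deaths, from first dose to 30 days after last dose, will be tabulated regardless of attribution. Report the number of participants with at least one event, and maximum grade per participant by type. Put the related-only tables beside them, and show events due to disease progression, as described in 8.4, on a separate line. Say in 10.5.4 what toxicity covers, so that it agrees with 10.1.

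Keep grade 2 laboratory events related-only, because 6.1 does not fully record unrelated grade 1-2 laboratory values and an all-cause table would be incomplete.

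The cost is wording in two sections and a few extra tables from data already collected. No visit, sample or participant is added. The all-cause rates will look less favourable and will include disease-driven events; the separate progression line and the related-only tables let a reader see how much.

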#### 10.2 STATISTICAL HYPOTHESIS

## 10.2.1 Primary Efficacy endpoints:

Disease control rate defined as (CR+PR+ stable x 16 weeks) using RECIST criteria.

## 10.2.2 Secondary Efficacy endpoints:

- Safety of Minnelide
- PFS and OS

#### 10.3 SAMPLE SIZE DETERMINATION

The primary objective of this trial is to determine if the CR, PR and SD > 16 weeks (clinical benefit) rate will be adequate using Minnelide without stratification for dose. The trial will be conducted using a Simon optimal two-stage phase II trial design [20][19] to rule out an unacceptably low clinical benefit rate of 20% (p0=0.20) in favor of an improved clinical benefit rate of 40% (p1=0.40). With alpha=0.10 (probability of accepting a poor treatment=0.10) and beta=0.20 (probability of rejecting a good treatment=0.20), the first stage will enroll a total of 12 evaluable participants. If 0-2 of these 12 participants have clinical benefit, then no further participants will be accrued. If 3 or more of the first 12 participants have clinical benefit, then accrual would continue until a total of 25 evaluable participants have been enrolled. As this is a rare participant population, trial accrual may continue for up to 15 participants while this determination is being made, but no new participants may be accrued to the trial once it is known that this criteria has not been met. If single agent activity is insufficient to meet criteria for study continuation, consideration will be given to exploring combination therapy including Minnelide in this population. If there are 3-7 participants with clinical benefit out of 25 participants, this would be an uninterestingly low clinical benefit rate. If there are 8 or more of 25 (32%) who experienced clinical benefit, this would be sufficiently interesting to warrant further study in later trials. Under the null hypothesis (20% clinical benefit rate), the probability of early termination is 55.8%.

It is expected that approximately one participant may initiate treatment on this trial every 1-2 months; thus, accrual to the trial may be completed in 3 years. In order to allow for screen failures and a small number of inevaluable participants, the accrual ceiling will be set at 55 participants.

#### 10.4 POPULATIONS FOR ANALYSES

Intention to treat: any participants who enroll onto the trial and provide consent and who receive at least one dose of the assigned agent will be included in the efficacy and safety evaluations.

Version Date: 7/10/2025

## **10.4.1** Evaluable for toxicity

All participants will be evaluable for toxicity from the time of their first treatment with Minnelide.

## **10.4.2** Evaluable for objective response:

Only those participants who have measurable disease present at baseline, have received at least one cycle of therapy, and have had their disease re-evaluated will be considered evaluable for objective response. These participants will have their response classified according to the definitions stated below. (Note: Participants who exhibit objective disease progression prior to the end of cycle 1 will also be considered evaluable.)

## **10.4.3** Evaluable Non-Target Disease Response:

Participants who have lesions present at baseline that are evaluable but do not meet the definitions of measurable disease, have received at least one cycle of therapy, and have had their disease reevaluated will be considered evaluable for non-target disease. The response assessment is based on the presence, absence, or unequivocal progression of the lesions.

